2.1.5.2. Secondary Estimands: Infant Participants

- **Functional antibody levels estimated by the GMT for RSV A– and RSV B–neutralizing antibody titers.**

This estimand estimates the vaccine effect in the hypothetical setting where participants follow the study schedules and protocol requirements as directed. It includes the following 4 attributes:

- Population: Infants born to maternal participants receiving 1 dose of investigational product and in compliance with key protocol criteria (evaluable participants).
- Variable: Antibody titers at birth and at 1, 2, 4, and 6 months of age.
- Intercurrent event(s): For participants who discontinue or have major protocol violations, all postdiscontinuation or postviolation observations will be censored. Results obtained from out-of-window blood draws will also be removed. Missing serology results will not be imputed, as MCAR is assumed.
- Population-level summary: GMT for RSV A– and RSV B–neutralizing antibody titers.

- **GMR estimated by the ratio of the GMT for RSV A– and RSV B–neutralizing antibody titers of the RSV vaccine group to the placebo group.**

This estimand estimates the vaccine effect in the hypothetical setting where participants follow the study schedules and protocol requirements as directed. It includes the following 4 attributes:

- Population: Infants born to maternal participants receiving 1 dose of investigational product and in compliance with key protocol criteria (evaluable participants).
- Variable: Antibody titers at birth and at 1, 2, 4, and 6 months of age.
- Intercurrent event(s): For participants who discontinue or have major protocol violations, all postdiscontinuation or postviolation observations will be censored. Results obtained from out-of-window blood draws will also be removed. Missing serology results will not be imputed, as MCAR is assumed.
- Population-level summary: GMR estimated by the ratio of the GMT for RSV A– and RSV B–neutralizing antibody titers of the RSV vaccine group to the placebo group.

CCI

CCI

CCI

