4. ANALYSIS SETS (POPULATIONS FOR ANALYSIS)

Data for all participants will be assessed to determine if participants meet the criteria for inclusion in each analysis population prior to unblinding and releasing the database and classifications will be documented per standard operating procedures.

Population	Description
Enrolled	All participants who sign the informed consent document.
Randomly assigned to investigational product	All maternal participants who are assigned a randomization number in the interactive response technology (IRT) system.
Evaluable – Maternal	All maternal participants who: 
 • are eligible; • receive the investigational product to which they were randomized; • have blood drawn for assay testing within the protocol-specified time frames ; • have at least 1 valid and determinate assay result after vaccination; and • have no major protocol violations. Participants will be analyzed according to the investigational product as randomized.
Evaluable – Infant	All infant participants who: 
 • are eligible; • are born to the maternal participants who received the investigational product to which they were randomized and who have no major protocol violations before delivery; • have blood drawn for assay testing within the protocol-specified time frame at birth^a; • have at least 1 valid and determinate assay result at birth^a; and • have no major protocol violations. Participants will be analyzed according to the investigational product as randomized to their mothers.
Modified intent-to-treat (mITT) – Maternal	All randomized maternal participants who receive investigational product and have at least 1 valid and determinate assay result for the proposed analysis. Participants will be analyzed according to the investigational product as randomized.
mITT – Infant	All infant participants who are born to vaccinated maternal participants and have at least 1 valid and determinate assay result for the proposed analysis. Participants will be analyzed according to the investigational product as randomized to their mothers.
Safety – Maternal	All randomized maternal participants who receive investigational product. Participants will be analyzed according to the investigational product they actually received. A randomized participant who did not receive investigational product will be excluded from the safety analyses.

Population	Description

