Safety – Infant	All infant participants who are born to vaccinated maternal participants. Participants will be analyzed according to the investigational product their mothers actually received. An infant born from a randomized maternal participant who did not receive investigational product will be excluded from the safety analyses.

- a. Cord blood sample must be obtained on the day of birth. If cord blood is unavailable, a venous blood sample is to be collected up to 24 hours after birth.

Major protocol violations will be determined by clinical review (through the data handling memo). A major protocol violation is a protocol violation that, in the opinion of the sponsor’s study medical monitor, would materially affect assessment of immunogenicity, eg, participant receipt of a prohibited vaccine or medication that might affect immune response or a medication error with suspected decrease in potency of the vaccine. The sponsor’s medical monitor will identify those participants with protocol violations before any immunogenicity analysis is carried out.

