5.2.2.1. Geometric Mean Titer (GMT)

Continuous immunogenicity endpoints will be logarithmically transformed for analysis. GMT and associated 2-sided 95% CI will be calculated at each available time point for each vaccine group. 95% CI will be calculated by back transformation of the 95% CI for the mean of the logarithmically transformed assay results computed using Student's t distribution.

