5.2.2.3. Geometric Mean Ratio (GMR)

The GMR will be calculated as the group mean difference of logarithmically transformed antibody levels and back transformed to the original units. Two (2)-sided 95% CI is also computed by back transformation of the CIs using 2-sample Student's t distribution for the mean difference of the logarithmically transformed assay results.

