6.2.2.1.1. Main Analysis

- Estimand strategy: Hypothetical.
- Analysis set: Evaluable ([Section 4](#)). Infant participants born to maternal participants receiving 1 dose of investigational product and in compliance with the key protocol criteria.

- Analysis methodology: Descriptive summary statistics.
- Intercurrent events and missing data: All postdiscontinuation or postviolation observations will be censored. Results obtained from out-of-window blood draws will also be removed. Missing data will not be imputed.
- GMTs of the RSV A– and RSV B–neutralizing antibody titers at each available time point will be descriptively summarized for each vaccine group, along with associated 2-sided 95% CIs.
- GMRs of the RSV vaccine group to the placebo group for the RSV A– and RSV B–neutralizing antibody titers at each available time point after birth will be calculated, along with associated 2-sided 95% CIs.
- RCDCs for RSV A– and RSV B–neutralizing antibody titers for a combination of prespecified time points and vaccine groups will be generated.

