6.2.2.1.2. Supplementary Analysis

The main analysis will also be performed based on the mITT population if there is enough difference between the mITT population and the evaluable population. This analysis will be performed only if there is enough difference (eg, ~10%) between the evaluable immunogenicity population and the mITT population.

In addition, GMTs of cord blood and GMTs of venous blood obtained within the first 24 hours after birth, along with associated 95% CIs, will be presented by maternal vaccine group. This analysis will be performed only if there is a sufficient number of cases in which venous blood was collected (eg, ~10%).

CCI

CCI

CCI

CCI

CCI

CCI

CCI

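### The infant evaluable set requires a valid birth result, so usable 1- to 6-month titers are left out of main summaries that do not use the birth value: a modest, avoidable loss of precision

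*SAP*

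**What the plan says.** **The set.** In SAP Section 4, Evaluable – Infant requires a birth sample drawn in the protocol time frame, and the infant must "have at least 1 valid and determinate assay result at birth". The footnote counts cord blood from the day of birth and adds: "If cord blood is unavailable, a venous blood sample is to be collected up to 24 hours after birth". A valid result at a later visit gives no way in. The Evaluable – Maternal row is not tied to one visit. Besides draws within the protocol time frames, it asks that participants "have at least 1 valid and determinate assay result after vaccination".

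**Its use.** SAP 6.2.2.1.1 names this set for the infant main analysis at all visits. GMTs are listed by time point, and GMRs for "antibody titers at each available time point after birth will be calculated".

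**The estimators.** SAP 5.2.2.1: "GMT and associated 2-sided 95% CI will be calculated at each available time point for each vaccine group". SAP 5.2.2.3: "The GMR will be calculated as the group mean difference of logarithmically transformed antibody levels and back transformed to the original units". Neither uses an earlier value from the same infant.

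**The protocol.** Section 9.3 ties the infant evaluable set to valid results for whichever analysis is proposed, not to birth.

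**Recovery.** SAP 6.2.2.1.2 provides a modified intent-to-treat (mITT) rerun, with a condition: "This analysis will be performed only if there is enough difference (eg, ~10%) between the evaluable immunogenicity population and the mITT population". SAP 6.4 restricts the immunogenicity subgroups to the evaluable set, while leaving room for further undefined analyses.

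**The concern.** Infant titers through 6 months are the infant secondary endpoint and describe how long transferred antibody persists. The data at those visits are already thin, because Protocol 1.3.2 has each infant sampled at only two of the four later visits. The rule sets aside valid observations at exactly those visits, in summaries that have no need of the birth value.

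The affected group is foreseeable:

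- Both documents anticipate unavailable cord blood.
- Protocol Table 5 allows no venous draw below 1.3 kg.
- SAP 5.3.2 sets insufficient, indeterminate and undone assays to missing.

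The study is descriptive, but the SAP Introduction says it will supply the data for choosing dose and formulation, so the precision of these estimates has some value.

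**Working it through.** **Does a later-visit summary need the birth result?** The GMT interval is a one-sample t interval on the log titers at that visit. The GMR interval is a two-sample t interval on the same kind of data. SAP 6.2.2.1.1 lists no infant fold rise from birth. The birth result therefore affects only who is counted.

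**Size.** The plan states no precision for infant titers. Its only sample-size figure, Protocol Table 6, concerns adverse events; it reproduces (1 − 0.99^100 = 0.634, stated as 63%) but does not bear on this point. What follows is an illustration.

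Inputs from the documents:

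- Up to 650 women in five equal groups (Protocol 9.2), singleton pregnancies (5.1.1).
- About 500 northern and up to 150 southern (Protocol 4.1.2).
- Two infant sampling schedules (Protocol 1.3.2).
- Four gestational-age bands (SAP Tables 8 and 9).

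Assumed:

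- An even schedule split, even allocation within hemisphere, and an even spread over the bands.
- A share m of infants without a valid birth result. The documents give no figure.
- Every affected infant later gives a valid in-window titer. This makes the results upper bounds for a given m.

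Formulas, with s the SD of log titer, which cancels in the ratio of widths:

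- GMT half-width = t(0.975, n − 1) × s/√n
- GMR half-width = t(0.975, 2n − 2) × s × √(2/n)
- n′ = n × (1 − m)

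Infants per arm per later visit: main 650/5/2 = 65; northern 500/5/2 = 50; southern 150/5/2 = 15; gestational-age band 65/4 = 16.25.

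Two GMT examples:

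- Main, m = 9%: n = 65 gives 1.998/√65 = 0.2478; n′ = 59.15 gives 2.002/√59.15 = 0.2603; ratio 1.050.
- Southern, m = 20%: n = 15 gives 2.145/√15 = 0.5538; n′ = 12 gives 2.201/√12 = 0.6354; ratio 1.147.

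| Analysis | n | m | n′ | GMT interval wider by | GMR interval wider by |
|---|---|---|---|---|---|
| Main | 65 | 5% | 61.8 | 2.7% | 2.7% |
| Main | 65 | 9% | 59.2 | 5.0% | 4.9% |
| Southern | 15 | 5% | 14.3 | 3.1% | 2.9% |
| Southern | 15 | 10% | 13.5 | 6.6% | 6.0% |
| Southern | 15 | 20% | 12.0 | 14.7% | 13.2% |
| Northern | 50 | 5% | 47.5 | 2.7% | 2.7% |
| Northern | 50 | 10% | 45.0 | 5.7% | 5.6% |
| Northern | 50 | 20% | 40.0 | 12.5% | 12.2% |
| GA band | 16.25 | 5% | 15.4 | 3.1% | 2.8% |
| GA band | 16.25 | 10% | 14.6 | 6.5% | 5.9% |
| GA band | 16.25 | 20% | 13.0 | 14.5% | 13.1% |

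At m = 9%, 0.09 × 650 = 58.5, so about 58 infants and up to about 116 later draws would be outside the main summaries.

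The main rows stop at 9% because from about 10% the mITT rerun applies. The trigger is approximate, so 9% might also prompt it, and exclusions for other reasons could bring it on sooner. The subgroups have no prespecified mITT version in the visible text.

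**The case against.** The strongest defence is that this is a permitted convention. Protocol Section 9 lets the SAP modify the plan, and the SAP version table shows that the infant row was revised on purpose. SAP 3.4.2 makes birth the infant baseline. In SAP 2.1.5.2 the estimand's population is the evaluable participants, in a setting where the schedule is followed, and a birth sample is part of that schedule. All of this stands. It rules out reading the set as a contradiction of the estimand. The intercurrent-event text there does not itself call for the exclusion, however. It handles single results ("Results obtained from out-of-window blood draws will also be removed") and leaves missing ones unimputed under MCAR.

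A second defence is that one cohort followed from birth keeps a change of infants apart from antibody decline. This stands in part: under the current rule every later-visit infant is eligible for the birth GMT. But the split schedule already puts different infants at the 1/4-month and 2/6-month visits, so the series is not one fixed cohort.

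Third, redacted SAP text may hold a reason for the rule or analyses that use the birth value. That is possible, but the visible later-visit GMTs, GMRs and curves do not use it.

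A reader might go further and infer three things that the documents do not support:

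- **Biased later-visit GMTs.** That needs birth-sample loss related to titer. The plan assumes MCAR, and nothing shows otherwise.
- **Infants lost for good from the subgroup results.** No prespecified subgroup includes them, but SAP 6.4 and 7.2 allow additional analyses.
- **A changed dose choice.** SAP 5.1 uses no decision rules, and the Introduction places the development criteria outside the SAP.

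**Conclusion.** The point holds as an avoidable loss of precision, not as an error and not as a shown bias. Valid later titers are left out of the main later-visit summaries because of a birth result that those summaries do not use. Under the plan's own MCAR assumption, including them would narrow the intervals without introducing bias.

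The gain is modest. In the main analysis it is about 3% to 5% of GMT interval width for assumed missing rates of 5% to 9%. The larger figures, 12% to 15%, need 20% missing and apply to descriptive subgroups. All sizes rest on assumed rates, maximum enrolment, even splits and full later sampling of the affected infants. The 24-hour venous fallback should keep the group small, and SAP 6.5.2 reports exclusions with reasons, so the actual loss would be visible. The change is worth making because it is cheap.

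**What to change.** Define infant evaluability by time point in SAP Section 4. At a given visit an infant is included if:

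- the infant is eligible;
- the mother received the randomized product and had no major protocol violation before delivery;
- the infant has no major protocol violation; and
- there is an in-window, valid and determinate result at that visit.

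Keep the birth-result requirement for analyses that use the birth value: the birth GMT and GMR, the placental transfer ratio, and any analysis with birth as baseline. The subgroups in SAP 6.4 would then follow the by-visit set without further edits.

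Add a sensitivity summary in infants with both a birth and a later result. It covers the main downside: N will vary by visit, and later GMTs will include some infants absent from the birth GMT, so a birth-to-later comparison could mix a small change of cohort with antibody decline.

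The cost is a one-row SAP edit, programming by visit, and one extra table.

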5. GENERAL METHODOLOGY AND CONVENTIONS

5.1. Hypotheses and Decision Rules

This Phase 2 study is designed to describe the safety, tolerability, and immunogenicity of RSV vaccine formulations in maternal participants and their infants. No formal statistical hypothesis testing will be performed. An estimation approach will be used to assess the safety and immunogenicity objectives.

Statistical decision rules will not be utilized in this study. All analyses are considered descriptive in nature.

5.2. General Methods

Descriptive summary statistics will be provided for all endpoints. Unless otherwise explicitly stated, descriptive statistics for continuous variables are n, mean, median, standard deviation, minimum, and maximum. Descriptive statistics for categorical variables are the proportion (%) and the n (the numerator) and N (the denominator) used in the calculation of the proportion.

All analyses for both immunogenicity and safety data will be descriptive in nature.

All of the safety, tolerability, and immunogenicity data will be summarized by vaccine group of the maternal participants. Immunogenicity results will be analyzed separately for all the formulations. Within each participant group (maternal or infant), all participants who receive placebo will be combined as the control group. All data will be presented separately for maternal and infant participants. The only exception is the combined analysis of maternal-to-infant placental transfer ratio (infant/mother) of RSV A– and RSV B-neutralizing antibody titers.

Within maternal and infant groups, immunogenicity results may be summarized by formulation, dose level, and gestational age (GA).

5.2.1. Analyses for Binary Endpoints

The number and percentage of participants in each category will be summarized. The 95% CI for percentage, and for the difference in percentages, will also be presented, where appropriate.

The 95% CI for the proportion will be constructed by the Clopper-Pearson method described by Newcombe.¹ The 95% CI will be presented in terms of percentage.

The 95% CI for the difference in the proportions will be computed using the Chan and Zhang method.² The 95% CI will be presented in terms of percentage.

5.2.2. Analyses for Continuous Endpoints

Unless otherwise specified, the CI for the mean of the continuous variables will be constructed by the standard method based on Student's t distribution.

5.2.2.1. Geometric Mean Titer (GMT)

Continuous immunogenicity endpoints will be logarithmically transformed for analysis. GMT and associated 2-sided 95% CI will be calculated at each available time point for each vaccine group. 95% CI will be calculated by back transformation of the 95% CI for the mean of the logarithmically transformed assay results computed using Student's t distribution.

5.2.2.2. Geometric Mean Fold Rise (GMFR)

GMFR will be calculated as the mean difference of an individual participant's logarithmically transformed antibody levels (postvaccination minus prevaccination) and back transformed to the original units. 95% CI will be computed by back transformation of the 95% CI using 1-sample Student's t distribution for the mean difference of the logarithmically transformed assay results.

5.2.2.3. Geometric Mean Ratio (GMR)

The GMR will be calculated as the group mean difference of logarithmically transformed antibody levels and back transformed to the original units. Two (2)-sided 95% CI is also computed by back transformation of the CIs using 2-sample Student's t distribution for the mean difference of the logarithmically transformed assay results.

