- Perform obstetric examination including but not limited to fundal height, fetal heart tones, and fetal movement.
- Ensure that all inclusion criteria and none of the exclusion criteria are met.
- Ensure that the maternal participant meets none of the temporary delay criteria as described in [Section 5.2.3](#).
- Ask the maternal participant to provide a urine sample for glucose and protein testing (urine dipstick).

- Issue the maternal participant an e-diary and provide instructions on its completion.
- Prior to vaccination, collect a blood sample of approximately 25 mL for serologic assessments.
- Obtain the maternal participant's randomization number and investigational product kit number using the IRT system. Either blinded or unblinded site staff may obtain this information. The infant blood sample schedule will be provided at this time. Refer to the IRT manual for further instructions on this process.
- Unblinded site staff member(s) will administer a single 0.5-mL dose of investigational product into the deltoid muscle of the nondominant arm. Please refer to the IP manual for further instruction on this procedure.
- Blinded site staff must observe the maternal participant for any acute reactions for at least 30 minutes after investigational product administration.
 - **Note:** The first 5 maternal participants vaccinated in the study will be observed for at least 4 hours after investigational product administration.
- Record any acute reactions in the maternal participant's source documents, on the AE page of the CRF, and on an SAE form as applicable.
- Issue a measuring device to measure local reactions and a digital thermometer for recording daily temperatures, and provide instructions on their use.
- Ask the maternal participant to complete the e-diary from Day 1 to Day 7, with Day 1 being the day of vaccination.
- Ask the maternal participant to contact the site staff or investigator immediately if she experiences any of the following from Day 1 to Day 7 after vaccination to determine if an unscheduled reactogenicity visit is required:
 - Fever $\geq 39.0^{\circ}\text{C}$ ($\geq 102.1^{\circ}\text{F}$).
 - Redness or swelling at the injection site on the nondominant arm measuring greater than 10 cm (>20 measuring device units).
 - Severe pain at the injection site on the nondominant arm.
 - Any severe systemic event.
 - Any blackening of the skin (necrosis) at the injection site.
 - Any peeling/scaling of the skin (exfoliative dermatitis).

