8.10.1.4. Maternal Participants: 1-Month Follow-up Visit (28 to 42 Days After Vaccination)

If delivery occurs before this visit, this visit will not be conducted.

- Ensure that the maternal participant continues to be eligible for the study and meets none of the participant withdrawal criteria as described in [Section 7.2](#).
- Measure vital signs, including oral temperature, seated blood pressure, and heart rate.
- Measure and record weight.
- Perform obstetric examination including but not limited to fundal height, fetal heart tones, and fetal movement.
- Collect a blood sample of approximately 25 mL for serologic assessments.
- Record details of any antenatal steroid treatment, monoclonal antibodies, blood transfusions (eg, whole blood, packed cells), or Rho(D) immune globulin (eg, RhoGam) given since the last visit.
- Record any medication taken to treat an AE since the last visit.
- Record details of any nonstudy vaccinations given since the last visit.
- Complete the maternal participant's source documents.
- Ask the maternal participant to contact the site staff or investigator if a medically attended event (eg, doctor's visit, emergency room visit) or hospitalization occurs.

- Record AEs as described in [Section 8.3](#) and [Section 10.3.3](#).
- The investigator or an authorized designee completes the CRF.

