3.4. Baseline Variables

3.4.1. Baseline Variables: Maternal Participants

Day 1 is defined as the day of vaccination and the start of the reporting period for local reactions and systemic events in the electronic diary (e-diary) for maternal participants.

Laboratory data will be collected for maternal participants only. Data are collected during the screening visit, Visit 0 (-14 to -2 days prior to vaccination), and will be considered baseline data.

Day 1 is considered the baseline visit for the following assessments: immunogenicity, obstetric examination, and vital signs.

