5.3.2. Immunogenicity Data

For GMT and GMC analysis, a titer reported as < lower limit of quantitation (LLOQ) will be converted to a value of $\frac{1}{2}$ LLOQ. For calculating a fold rise, < LLOQ will be converted to $\frac{1}{2}$ LLOQ for a numerator, and < LLOQ will be converted to LLOQ for a denominator when only one of either the numerator or denominator is < LLOQ. If both the numerator and denominator are < LLOQ, then both will be converted in the same way. For any calculations, a titer reported as > upper limit of quantitation (ULOQ) will be converted to a value of ULOQ.

Values that are designated as serum quantity not sufficient (QNS), designated as indeterminate results, or recorded as "Not Done" will be set to missing. No imputation will be done for these missing values.

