6.2.1.1.1. Main Analysis

- Estimand strategy: Hypothetical.
- Analysis set: Evaluable (Section 4). Maternal participants receiving 1 dose of investigational product and in compliance with key protocol criteria.
- Analysis methodology: Descriptive summary statistics.

- Intercurrent events and missing data: All postdiscontinuation or postviolation observations will be censored. Results obtained from out-of-window blood draws will also be removed. Missing results will not be imputed.
- GMTs of the RSV A– and RSV B–neutralizing antibody titers at each available time point will be descriptively summarized for each vaccine group, along with associated 2-sided 95% CIs.
- GMFRs and associated 2-sided 95% CIs will be provided for RSV A– and RSV B–neutralizing antibody titers from before vaccination to each available time point after vaccination for each vaccine group.
- GMRs of the RSV vaccine group to the placebo group for the RSV A– and RSV B–neutralizing antibody titers at each available time point after vaccination will be calculated, along with associated 2-sided 95% CIs.
- RCDCs for RSV A– and RSV B–neutralizing antibody titers for a combination of prespecified time points and vaccine groups will be generated.
- Bar graphs of prevaccination and 1-month-postvaccination neutralizing GMTs will be produced for each vaccine group.

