6.2.1.1.2. Supplementary Analysis

The main analysis will also be performed based on the mITT population if there is sufficient difference between the mITT population and the evaluable populations (an approximate 10% difference in the numbers of participants in each population).

The effects of formulation and dose on RSV A– and RSV B–neutralizing titers will be evaluated using an analysis of variance model with the log-transformed values of neutralizing titers at 1 month after vaccination. The model will include formulation and dose as main effects and their interaction. The F statistic and p-value for the main effects and interaction will be calculated. The least-square (LS) means, difference between the means, and 95% CI associated with these differences will be presented for each main effect. These will be exponentiated and presented in the original scale.

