6.4. Subset Analyses

Subgroup analyses of the secondary **CCI** immunogenicity endpoints will be performed, based on cohort (northern vs southern hemisphere), and subcategories of gestational age at the time of vaccination. Subgroup analyses for immunogenicity will be based on the respective evaluable immunogenicity population only. Table 8 and Table 9 summarize the defined subgroup analyses. Additional analyses (not defined here) may be performed if deemed necessary.

Table 8. Summary of Subgroup Analyses for Maternal Participants

Subgroup	Endpoints
Gestational age (GA) at the time of vaccination: 24 weeks ≤ GA <27 weeks 27 weeks ≤ GA <30 weeks 30 weeks ≤ GA <33 weeks GA ≥ 33 weeks	
 • RSV A– and RSV B–neutralizing antibody titers; C [REDACTED] • Combined RSV A/B–neutralizing antibody titers; C [REDACTED]
Cohort: Northern hemisphere Southern hemisphere	
 • RSV A– and RSV B–neutralizing antibody titers; C [REDACTED] • Combined RSV A/B–neutralizing antibody titers; C [REDACTED]

Table 9. Summary of Subgroup Analyses for Infant Participants

Subgroup	Endpoints
Maternal gestational age (GA) at the time of vaccination: 24 weeks ≤ GA <27 weeks 27 weeks ≤ GA <30 weeks 30 weeks ≤ GA <33 weeks GA ≥ 33 weeks	
 • RSV A– and RSV B–neutralizing antibody titers; C [REDACTED] • Combined RSV A/B–neutralizing antibody titers; C [REDACTED]

Table 9. Summary of Subgroup Analyses for Infant Participants

Subgroup	Endpoints
	C C [Redacted]
Cohort: Northern hemisphere Southern hemisphere	
 
• RSV A– and RSV B–neutralizing antibody titers; C I [Redacted] 
• Combined RSV A/B–neutralizing antibody titers; C C I [Redacted]
Birth after vaccination: ≤14 days and >14 days	CCI [Redacted]
Birth after vaccination: ≤30 days and >30 days	CCI [Redacted]

CCI [Redacted]

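### The vaccine-versus-placebo GMRs and the dose-by-formulation ANOVA use no baseline covariate in the readable text; they are valid but may be less precise than the planned data allow

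*SAP*

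**What the plan says.** SAP 5.2.2.3 defines the between-group measure: "The GMR will be calculated as the group mean difference of logarithmically transformed antibody levels and back transformed to the original units". Its interval comes from a two-sample t distribution. SAP 6.2.1.1.1 applies it to mothers ("GMRs of the RSV vaccine group to the placebo group") at each time point after vaccination. SAP 6.2.2.1.1 does the same for infants at each time point after birth. Neither names a covariate.

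SAP 6.2.1.1.2 adds an analysis of variance of log titer at 1 month after vaccination: "The model will include formulation and dose as main effects and their interaction". No other term is listed.

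The baseline data are planned. Protocol 8.10.1.2 (Vaccination, Day 1) instructs: "Prior to vaccination, collect a blood sample of approximately 25 mL for serologic assessments". SAP 3.4.1 states: "Day 1 is considered the baseline visit for the following assessments: immunogenicity, obstetric examination, and vital signs". SAP 6.4 defines subgroups "based on cohort (northern vs southern hemisphere), and subcategories of gestational age at the time of vaccination". In the readable text the Day 1 titer appears in the baseline GMTs, the bar graphs and the within-group fold rises (SAP 5.2.2.2). Gestational age and hemisphere appear only as subgroup splits. None of them enters a between-group estimate.

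**The concern.** SAP section 2 says the study is to supply the data for choosing dose and formulation, and leaves the decision criteria outside the SAP. SAP 5.1 takes an estimation approach without hypothesis tests, so interval width is the main measure of what the study shows. The ANOVA is the only readable analysis that contrasts doses and formulations directly. The GMRs are all against placebo and inform that choice only indirectly.

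Protocol 2.3 describes pregnant women as universally RSV-experienced, so mothers will enter with existing antibody, and some correlation between baseline and post-vaccination titer is plausible. If it exists, leaving the Day 1 titer out gives wider intervals than the same data could support.

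A second, smaller issue concerns missing data. For the 1-month visit, Protocol 8.10.1.4 says: "If delivery occurs before this visit, this visit will not be conducted". Absent 1-month samples therefore depend on gestational age at vaccination, while SAP 2.1.5.1 assumes titers are missing completely at random (MCAR).

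**Working it through.** **The plan's own figure.** The documents give no precision figure for a GMR or for the ANOVA. The only sample-size figure is Protocol Table 6, on adverse events. Its worked example reproduces: 1 − (1 − 0.01)^100 = 0.634, stated as 63%. It says nothing about titers.

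**Inputs.**
- Arms: five, equal allocation, up to 650 mothers (Protocol 1.1 and 9.2), so at most 650/5 = 130 per arm. Table 6 uses 100 per arm.
- ANOVA main effect: two vaccine arms against two, at most 260 v 260. SAP 6.2.1.1.2 does not say how placebo is handled; the four vaccine arms are assumed.
- SD of ln titer: not given; assumed 0.9, range 0.7 to 1.1.
- rho: not given; assumed 0 to 0.7.

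**Formulas.** The 95% interval is the estimate x/÷ exp(t × SD × √(1 − rho²) × √(2/n)), with rho = 0 for the unadjusted analysis. The log-scale width ratio, adjusted to unadjusted, is √(1 − rho²).
- GMR, unadjusted: 1.969 × 0.9 × √(2/130) = 0.2198; exp(0.2198) = 1.246.
- GMR at rho 0.5: 0.2198 × 0.866 = 0.1904; exp(0.1904) = 1.210.
- Main effect, unadjusted: 1.965 × 0.9 × √(2/260) = 0.1551; exp(0.1551) = 1.168.
- Main effect at rho 0.5: 0.1551 × 0.866 = 0.1343; exp(0.1343) = 1.144.

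| rho | width ratio | GMR factor, 130 v 130 | main-effect factor, 260 v 260 |
|---|---|---|---|
| 0 | 1.000 | 1.246 | 1.168 |
| 0.3 | 0.954 | 1.233 | 1.159 |
| 0.5 | 0.866 | 1.210 | 1.144 |
| 0.7 | 0.714 | 1.170 | 1.117 |

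For SD 0.7 to 1.1 the main-effect factor is 1.128 to 1.209 unadjusted and 1.110 to 1.178 at rho 0.5. At Table 6's 100 per arm, with SD 0.4 on the log10 scale (0.4 × 2.303 = 0.92 ln), the GMR factor is 1.293 unadjusted and 1.250 at rho 0.5. That gain equals having 100/(1 − 0.25) = 133 per arm.

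**Validity and robustness, by simulation.** With 4,000 simulated trials per setting, the unadjusted interval covered 0.947 to 0.955 with no material bias. The adjusted interval covered 0.948 to 0.952. At rho 0 the width ratio was 1.003, so a useless covariate costs almost nothing. With unequal correlations in the two arms (0.8/0.4 and 0.9/0.2) the ratio was 0.802 and 0.837. This agrees with √(1 − r²), where r is the average of the two correlations: 0.800 at 0.6 and 0.835 at 0.55.

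**Change from baseline is not a substitute.** A ratio of fold rises has variance 2(1 − rho) relative to the unadjusted comparison: 1.4 at rho 0.3, 1.0 at 0.5 and 0.6 at 0.7. It is worse than no adjustment when rho is below 0.5.

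**Missing Day 1 titers.** A complete-case adjusted model that loses a share m of mothers has relative variance (1 − rho²)/(1 − m). Break-even is m = rho²: 9%, 25% and 49% at rho 0.3, 0.5 and 0.7.

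**Missing 1-month titers.** The visit window opens at day 28. Mothers vaccinated at 33 0/7 to 36 0/7 weeks are then at 37 0/7 to 40 0/7 weeks. Skipped visits should therefore fall mainly in the last gestational-age band of SAP Table 8.

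**The case against.** The strongest reply is that nothing here is an error. The study has no hypothesis, decision rule or precision target; all analyses are labeled descriptive; and the estimand is a ratio of GMTs, which SAP 5.2.2.3 estimates directly. That is right, and it limits the point to precision.

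The gain is also assumed. The range includes zero, and no changed decision can be shown. For the ANOVA, only the correlation within the vaccine arms counts, so the larger gains seen when placebo has a high correlation do not carry over; at rho 0.3 the gain there is 4.6%. Both statements stand.

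The redactions matter too. A run of blacked-out text separates SAP 6.2.2.1.2 from 6.4, and Protocol 9.4.1 is cut within the fold-rise method. An adjusted model could be there. The claim can cover the readable text only.

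Further, gestational-age subgroup results are already planned, the missing-data remark is separate from precision, and the 130-per-arm example ignores the missing samples it predicts. The gains from gestational age, from hemisphere and for infant titers are not quantified. The proposal adds a second set of estimates and fills in missing baselines where the SAP says of unusable results: "No imputation will be done for these missing values". These are fair limits on size and cost. They do not remove the case for using a covariate the trial already plans to collect: subgroup tables and within-group fold rises give no adjusted between-group estimate.

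**Conclusion.** The concern holds as a recommended improvement. In the readable text, neither the GMRs nor the ANOVA uses the Day 1 titer, gestational age or hemisphere. The planned results are valid under randomization and the SAP's own missing-data assumption.

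For maternal comparisons the possible narrowing of the log-scale interval runs from nothing at rho 0 to 28.6% at rho 0.7, and is 13.4% at rho 0.5. In ratio terms the effect on a dose or formulation contrast is modest, for example 1.168 to 1.144. These figures depend on an assumed SD, an assumed correlation and full enrollment. Confidence is medium because of those assumptions and the redactions. The MCAR remark is secondary: conditioning on gestational age needs a somewhat weaker assumption.

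**What to change.** Before the first unblinded analysis (the earliest listed in SAP 7.2), add a prespecified linear model of log titer beside the unadjusted GMRs and ANOVA:

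- **Terms:** vaccine group (or dose, formulation and interaction), log Day 1 maternal titer, gestational age at vaccination and hemisphere.
- **Infants:** use the same maternal covariates for birth titers. Do not adjust for cord blood. SAP 3.4.2 calls it the infant baseline, but it is measured after vaccination and carries the vaccine effect.
- **Missing Day 1 titer:** state a rule, for example the overall mean log Day 1 titer, set blind to group, so that no mother is dropped. SAP section 4 requires a valid result only after vaccination, so such mothers can be in the evaluable set.
- **Placebo comparisons:** allow the baseline slope to differ by arm through a centered baseline-by-group term, or use robust standard errors.
- **Keep** the unadjusted GMTs and GMRs as descriptive output.
- **If a redacted section already contains this model,** refer to it from SAP 5.2.2.3 and 6.2.1.1.2.

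The cost is SAP wording, a standard model and additional tables, with no new samples. The two technical downsides, missing baselines and unequal slopes, are covered by the rules above.
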